#### **6.2 Analysis Plan**

Primary Hypothesis: Ha1a

We will calculate the proportion of trainees with template use and provide 95% confidence intervals with exact method, then we will test the hypothesis using a proportion test.

Secondary Hypotheses

Ha1b: Trainee and faculty confidence will increase after training for  $\geq 50\%$  of participants.

We define increased confidence as trainee and faculty post-intervention confidence scores of 4 or 5 on a 5-point Likert scale. We will calculate proportion of subjects who have increased confidence and show 95% confidence intervals as well, then we will use a proportion test for the hypothesis.

**Ha1c: Observed communication skills scores at the second and third simulated patient encounter will improve over the first encounter.**

The observed communication skills scores have three different scores (two sub-scores and one combined/total score). We will apply a linear mixed model with random subject effect to test whether each of three scores are different from encounter 1 to 2 and 3 separately. P-values will be adjusted for multiple tests by the Dunnett method.

**Ha2a: Trainees in the top half of template users will have higher total emotion-regulation competences (TOTAL) than trainees in the bottom.**

The ERSQ yields 10 different scales of emotion regulation: 9 specific competences and 1 TOTAL competency which is the average of the nine scales. We will provide summary statistics (mean and standard deviation) of TOTAL competency and use a two-sample t-test to test differences between the top half and low half groups of patients. P-value will be presented.

**Ha2b: Trainees in the top half of template users will have lower Emotional Exhaustion (EE) scores than trainees in the bottom half.**

We will provide summary statistics (mean and standard deviation) of EE scores and use a two-sample t-test to test differences between the top half and low half groups of patients. P-value will be presented

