### 1.2 Study Assessment Tools

Confidence Survey – Using a 5 point Likert scale (i.e. 1=strongly disagree, 2=disagree, 3=neutral, 4=agree 5=strongly agree) participants were asked to rate their confidence in various communication skills domains pre- and post-intervention via online survey.

Emotion Regulation Skills Questionnaire (ERSQ) – This validated instrument consists of 27 items, and includes subscales related to nine competencies of coping with negative emotion (awareness, sensations, clarity, understanding, acceptance, tolerance, readiness to confront, compassionate self-support and modification) which can be summed to a total score (TOTAL). The ERSQ assesses each skill by means of three items introduced by the phrase "In the last week..." and answered on a 5-point Likert-scale. Higher scores indicate stronger emotion regulation skills. We will administer the ERSQ via online survey.

Maslach Burnout Inventory™(MBI) – This validated, psychological inventory consists of 22 items related to occupational burnout, and includes subscales related to Emotional exhaustion (EE; 9 items), Depersonalization (DP; 5-items), and Personal Accomplishment (PA; 8 items). The MBI assesses each item on a 7-point Likert-scale. Higher scores indicated greater burnout. . We will use the MBI / Human Services Survey for Medical Personnel administered via online survey.

Semi-structured interview – At 6 months, participants (e.g. trained faculty, residents, and fellows) are asked a series of preselected questions in a one-on-one interview about their experience with the training, using the SICG with patients, benefits and difficulties of the training in the clinical setting.

**Serious Illness Conversation Guide (SICG©)** – improve the timing, frequency, quality, and tolerability (for both patient and clinician) of patient-centered values and goals conversations for patients living with serious illness. The SICG© was co-produced by clinicians, patients, and families and is a checklist of best-practice communication steps for use in patients with serious illness.

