## 2 Study Objectives

### **Aim 1. Evaluate the efficacy of our multimodal communication skills training on trainee documentation, confidence and observed communication skills over 12 months.**

Hypotheses: Template use for both trainee subgroups will increase from zero after training for ≥50% of trainees (Ha1a). Trainee and faculty confidence will increase after training for ≥50% of participants (Ha1b). Observed communication skills scores at the second and third simulated patient encounter will improve over the first encounter. (Ha1c).

Rationale: Augmenting standard training with priming, structured documentation templates, documentation audit and feedback, and embedded faculty coaches, we hope to increase the effect of communication skills training on clinical behavior change.

Outcomes: Participant template use at 12 months (Primary). Trainee, post-intervention self-rated confidence and performance in simulated patient encounters (Secondary).

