### 3.3 Secondary Study Endpoints

Resident, Fellow and Faculty post-intervention self-rated confidence and performance in simulated patient encounters.

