### **5.1 Before Communication Training Activities**

Tier 1 (education-only subjects): Three to four weeks prior to the subject's two-week palliative care elective they will be sent an email to complete an online confidence survey. They will receive email reminders to complete the survey until survey is completed.

Tier 2 (education + behavioral subjects): Subjects will have reviewed and signed consent documentation. In addition to the above online confidence survey, they will also receive email to complete electronic ERSQ and MBI.

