### **5.2 Two week palliative care elective**

Tier 1 – Integrated into the two-week elective with the palliative care department, subjects undergo a 1) four-hour training focused on the SICG©; 2) two simulated patient encounters with trained actors and feedback provided after training, 3) participant sent electronic notification to take post intervention survey of confidence

Tier 2 – In addition to above, these subjects will also complete a Priming intervention. They will receive a list of patients whom 1) the study subjected documented at least one note on in the past and 2) have a high likelihood of serious illness as determined by a chart review process. This list will be shared securely through Dartmouth secure file electronically, and participants will be asked three questions for each patient: 1) "Does this patient have serious illness?"; 2) "Would you be surprised if this patient died in the next 12 months?"; 3) Would this patient benefit from a serious illness guide conversation?; 4) If you saw this patient again, would you use the serious illness conversation guide with him/ her? Subjects will be asked to review no more than 30 patients. Subjects will be asked to return the completed email via Dartmouth secure file share.

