### **5.3 Electronic communication every two months following completion of elective**

Tier 1 – Every two months after completing the training, participants will receive email compare his or her own documentation of the taught template to top and average performers (comparison results given are anonymous). Non-top and top performers will receive different messages, customized through pre-testing with non-study residents and fellows. For example: "Talking to patients about their values is important but can take some pre-visit planning. Choose a patient you will see in the next two weeks to use the SICG" (non top-performers) or "Good job! Talking to

patients about their values is important. The way we continue to improve is by having more conversations. Choose a patient you will see in the next two weeks to use the SICG.” (top-performers). At four months, subjects will be asked electronically to complete their final confidence survey.

Tier 2 – For this part of the study, identical to Tier 1

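### Ha1b claims a rise in confidence, but the rule that tests it looks only at the score after training

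*Combined protocol and SAP*

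**What the plan says.** Section 2 (Aim 1) states Ha1b as a change: "Trainee and faculty confidence will increase after training for ≥50% of participants". Section 6.2 repeats it and then gives the working definition: "We define increased confidence as trainee and faculty post-intervention confidence scores of 4 or 5 on a 5-point Likert scale". The proportion meeting that definition is reported with a 95% confidence interval and put to a proportion test. No other analysis of confidence is described, in section 6.2 or in the Study Summary.

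The endpoint lists speak only of the level after training. The Aim 1 outcomes read "Trainee, post-intervention self-rated confidence and performance in simulated patient encounters (Secondary", and section 3.3 reads "Resident, Fellow and Faculty post-intervention self-rated confidence and performance in simulated patient encounters".

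The surveys themselves cover both sides of the training. Under section 1.2, "participants were asked to rate their confidence in various communication skills domains pre- and post-intervention via online survey". The schedule for trainees has three surveys:

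- Section 5.1, three to four weeks before the elective: "they will be sent an email to complete an online confidence survey".
- Section 5.2, with the elective: "participant sent electronic notification to take post intervention survey of confidence".
- Section 5.3: "At four months, subjects will be asked electronically to complete their final confidence survey".

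**The concern.** The hypothesis concerns change within a person, while the definition concerns a level at one time. The two agree only if nobody starts at 4 or 5 and everyone who gains ends there. The documents state neither condition.

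Followed exactly, the plan could report that confidence rose when nobody's score moved, provided enough trainees were confident at the start. It could also miss a real gain among those who started low. Confidence is one of the three results by which Aim 1 judges the training, so a mislabelled result would support a wrong statement about its effect.

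The rule also leaves open which survey decides. There are two after training, and section 11.3 calls the one at three to four months the second confidence survey, although by the section 5 schedule it is the third.

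**Working it through.** **1. What the rule does to individual score pairs (before → after)**

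| Pair | Actual change | Counted as increased? |
|---|---|---|
| 4 → 4 | none | yes |
| 5 → 5 | none | yes |
| 5 → 4 | fall | yes |
| 2 → 3 | rise | no |
| 1 → 3 | rise | no |

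The rule errs in both directions. If every trainee moved from 2 to 3, it would record 0% increased.

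**2. Could an item score of 4 or 5 itself mean that confidence rose?** No. Section 1.2 has participants rate their confidence by domain before and after training on the same agreement scale, so the item measures level and not perceived change.

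**3. How often the test would succeed with no change at all**

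The plan gives no power figure for Ha1b to reproduce, and no significance level, sidedness, exact method or sample size for it. The inputs are:

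- Null proportion 50%: from Ha1b.
- One-sided exact binomial test at 2.5%: borrowed from the primary hypothesis in section 6.1 (assumption).
- n = 42: the trainee sample in section 6.1, with full response (assumption). As variants, n = 30 respondents (assumption), and n = 42 + 5 + 4 + 4 = 55, which adds the 13 faculty trained in the prior work of section 1.4 (assumption).
- b = share already at 4 or 5 before training, unchanged afterwards: not in the documents, so varied from 40% to 80%.

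The critical count k is the smallest value with P(X ≥ k | n, 0.5) ≤ 0.025. The chance of success is then P(X ≥ k | n, b), with X binomial.

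- n = 42: P(X ≥ 27) = 0.0442 is too large and P(X ≥ 28) = 0.0218 qualifies, so k = 28.
- n = 30: k = 21, actual level 0.0214.
- n = 55: k = 36, actual level 0.0150.

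| b | n = 42 (28 needed) | n = 30 (21 needed) | n = 55 (36 needed) |
|---|---|---|---|
| 40% | 0.04% | 0.09% | 0.01% |
| 50% | 2.2% | 2.1% | 1.5% |
| 60% | 24% | 18% | 25% |
| 70% | 74% | 59% | 81% |
| 80% | 99% | 94% | 99.6% |

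In every cell the true proportion whose confidence increased is 0%, so a test based on within-person change would never succeed.

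**The case against.** The best defence is that this is a labelling fault. The rule is explicit, fixed in advance and consistent with both endpoint statements, and reaching agreement on a confidence item is a legitimate outcome. That much stands, and it is why rewording alone would remove the contradiction. It does not justify calling a post-only score an increase, or testing a change hypothesis with it.

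The size is hypothetical. This also stands: no baseline distribution is given, the test settings are borrowed, and with half or fewer confident at the start the chance of a false claim is at most 2.2%. The n = 55 column adds little, because section 4.1 admits only residents and fellows.

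The wording of section 5.2 suggests that the survey at the elective is the deciding one. That is a fair reading, but the different count in section 11.3 shows the point is not settled.

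Two further points limit what a repair can do. Section 5 schedules no confidence survey for faculty, before or after training, so nothing can be concluded about them unless such data exist. And the comparison has no control group: even a paired analysis shows that confidence rose, not that the training caused it.

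**Conclusion.** The concern holds. As written, the Ha1b test estimates the share of participants who are confident after training and cannot support a claim that confidence increased. This follows from the wording alone and needs no assumption.

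How much it matters depends on a baseline share the documents do not give. Under the stated assumptions a false claim of increase is negligible at 40% already confident, close to the nominal level at 50%, and more likely than not at 70% for each sample size tried. The opposite error, missing real gains that end below 4, does not need a confident starting group.

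It should be fixed. Ha1b is secondary, so the damage is confined to what may be said about confidence.

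**What to change.** Choose one of two changes before the confidence data are analysed.

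**Preferred: test the change.**

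- Count a participant as increased if the score after training minus the score before is greater than 0.
- State how the domains are combined into one score. The mean of the confidence items is one option; the plan currently gives no rule.
- Name the deciding survey. The one at the elective is suggested, with the four-month survey reported descriptively.
- Test the proportion increased against 50% among participants with both surveys, as the only test of Ha1b, and state its level, sidedness and method.
- Describe the share at 4 or 5 before and after, and the number at the maximum before training.
- For anyone without a survey before training, including any faculty, report only the share at 4 or 5 afterwards where such data exist, with no claim of increase.

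**Minimum: keep the rule and change the claim.** Reword Ha1b and its label to 'confident after training', name the deciding survey, and drop the statement that confidence increased.

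**Cost.** For trainees either change is only SAP wording and an analysis of surveys already planned. The paired version loses participants without a baseline survey, possibly all faculty. Those already at the maximum cannot count as increased. A threshold just above 0 admits trivial gains, so it must be fixed before the data are seen.

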### **1.4 Prior Work**

Starting in 2017, we designed and implemented annual communication skills training. We trained 16 internal medicine residents (hereafter referred to as residents), 6 hematology-oncology fellows (hereafter referred to as fellows), and used a train-the-trainer model to train faculty attendings to serve as trainers in the clinical setting with trainees: 5 hospitalists, 4 primary care and 4 oncologists. We designed and embedded a template into the electronic medical record to standardize the documentation of the SICG. We developed a structured chart review protocol to identify outpatients with a high-likelihood of serious illness and evaluate trainee documentation habits

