## 4 Subject Selection and Withdrawal

### 4.1 Inclusion Criteria

All second-year internal medicine residents. All first-year hematology-oncology fellows.

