### **6 Statistical Plan**

#### **6.1 Sample Size Justification**

Primary Hypothesis: Template use for both trainee subgroups will increase from zero after training for  $\geq 50\%$  of trainee (Ha1a)

Let null hypothesis Hnull1a be  $p < 50\%$  and alternative hypothesis be Ha1a be  $p = p_1 \geq 50\%$ , where p is proportion of trainees who have any documented template use. Sample size of 42 (12 fellows and 30 eligible residents who have completed the education intervention by the end of the grant award period [June 2020]) enables us to have Minimum Detectable Difference (MDD) 19.05%, i.e., the least p1 is 69.05%, with 80% of power and 2.5% significance level using one-side proportion test with exact test.

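### Ha1b tests trainees and faculty trainers as one proportion, so a positive result need not mean that at least half of the trainees met the confidence criterion

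*Combined protocol and SAP*

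**What the plan says.** Section 6.2 states Ha1b as "Trainee and faculty confidence will increase after training for" at least half of the participants. The responder rule is common to both groups: "We define increased confidence as trainee and faculty post-intervention confidence scores of 4 or 5 on a 5-point Likert scale". The analysis is a single one: "We will calculate proportion of subjects who have increased confidence and show 95% confidence intervals as well, then we will use a proportion test for" Ha1b. No analysis by role is planned. The word pooled is not used, but one proportion and one test over both groups is the plain reading.

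The rest of the document disagrees on who belongs in this endpoint.

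- **Faculty included.** The Ha1b hypothesis in section 2 names trainees and faculty. Section 3.3 lists "Resident, Fellow and Faculty post-intervention self-rated confidence", together with performance in simulated encounters.
- **Trainees only.** The Aim 1 heading concerns trainees, and its outcome line reads "Trainee, post-intervention self-rated confidence and performance in simulated patient encounters (Secondary". Eligibility in 4.1 is "All second-year internal medicine residents. All first-year hematology-oncology fellows". The surveys and simulations in section 5 are built around the trainees' palliative care elective, and none is described for faculty. The sample size in 6.1 is 42, made up of 12 fellows and 30 residents.
- **Silent.** Section 6.3 defines populations for the primary outcome and for the emotion regulation and burnout outcomes, but none for confidence.

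On the role of faculty, section 1.4 says that the programme "used a train-the-trainer model to train faculty attendings to serve as trainers in the clinical setting with trainees".

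**The concern.** Aim 1 asks what the training does for trainees. The Ha1b proportion mixes them with the people trained to coach them. If the trainers score 4 or 5 more often than the trainees, they raise the pooled proportion with no change among trainees, and the report would give no trainee figure to show it.

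The responder rule adds to this. It is an absolute score after the intervention, not a change from baseline, so a faculty member who was already at 4 or 5 counts as a success.

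Because the sections disagree, the denominator is also open. An analyst could include or leave out faculty after seeing the data and cite the protocol for either choice.

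**Working it through.** **The plan's own figure.** None is given for Ha1b: no number of faculty, level, sidedness or choice of exact or approximate test. The nearest figure is for Ha1a in 6.1, "where p is proportion of trainees who have any documented template use": 42 trainees, one-sided exact 2.5%, 80% power, detectable proportion 69.05%. With a null of 50%, that level requires 28 of 42, and power at 69.05% is 69.7%. The stated 80% reproduces only at one-sided 5% (27 of 42, power 79.99%). That is a separate matter, but it is a reason to show both levels here.

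**Inputs.**

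- Trainees: 42 (6.1).
- Faculty: 5 + 4 + 4 = 13 (1.4). This is an assumption, because the count comes from prior work.
- Null proportion: 50% (Ha1b).
- Test: exact, one-sided 2.5%, borrowed from Ha1a (assumption).
- True trainee rate: 50% (assumption).
- Faculty rate of scores 4 or 5: not given, varied from 50% to 100%.

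**Step 1: cut-offs.** Take the smallest k with P(X ≥ k) ≤ 0.025 for X ~ Bin(n, 0.5).

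- n = 42: P(X ≥ 27) = 0.0442 and P(X ≥ 28) = 0.0218, so the cut is 28/42 (66.7%).
- n = 42 + 13 = 55: P(X ≥ 35) = 0.0290 and P(X ≥ 36) = 0.0150, so the cut is 36/55 (65.5%).

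**Step 2: chance of a positive pooled test.** With T ~ Bin(42, 0.5) and F ~ Bin(13, pF), the chance is P(T + F ≥ 36), the sum over f of P(F = f) × P(T ≥ 36 − f). At one-sided 5% the cut is 35/55.

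| Faculty rate pF | One-sided 2.5% | One-sided 5% |
|---|---|---|
| 50% | 1.5% | 2.9% |
| 70% | 6.8% | 11.3% |
| 80% | 12.3% | 19.1% |
| 90% | 20.7% | 30.0% |
| 100% | 32.2% | 43.9% |
| Trainees alone | 2.2% | 4.4% |

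**Step 3: trainees needed if all 13 faculty qualify.** 36 − 13 = 23, so 23/42 (54.8%) suffices instead of 28/42. With a true trainee rate of 45%, P(T ≥ 23) = 13.2%, against P(T ≥ 28) = 0.4% for trainees alone.

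**Step 4: an observed half of the trainees.** 21 + 13 = 34, and 34/55 = 61.8%. The exact one-sided p is 0.052 and the 95% interval is 47.7% to 74.6%. The exact test does not reject at 2.5% or at 5%. A z-test without continuity correction gives p = 0.040, which passes only at one-sided 5%.

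**Step 5: dependence on the number of faculty**, all qualifying, one-sided 2.5%, true trainee rate 50%.

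| Faculty | Pooled cut | Trainees needed | Chance of a positive test |
|---|---|---|---|
| 5 | 31/47 | 26/42 | 8.2% |
| 10 | 34/52 | 24/42 | 22.0% |
| 13 | 36/55 | 23/42 | 32.2% |
| 16 | 37/58 | 21/42 | 56.1% |
| 20 | 40/62 | 20/42 | 67.8% |

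The effect also grows if fewer trainees respond. With 22 trainees and 13 qualifying faculty, 11 + 13 = 24 of 35 passes (p = 0.0205).

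**The case against.** **The pooled hypothesis is what the plan wrote.** Ha1b is about participants, and both the hypothesis in section 2 and the endpoint in 3.3 name faculty. With trainees at 50% and faculty at 80% to 100%, the true pooled proportion is (21 + 10.4)/55 = 57% to (21 + 13)/55 = 62%, so the stated alternative is true. This stands. A reader might infer that the 12% to 32% are false-positive rates for Ha1b as written; they are not. They are the chance that the pooled test is positive while the trainee rate is only 50%, which matters because Aim 1 is framed on trainees.

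**Half of the trainees is not enough.** A reader might infer that faculty can carry the test when exactly half of the trainees are observed to qualify. With 42 trainees and 13 faculty this does not happen under the exact test (step 4). It would take at least 16 faculty, all qualifying, or far fewer trainee respondents.

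**Faculty may supply no data.** They are not eligible under 4.1 and section 5 gives them no survey. If they are never surveyed, the inflation is zero. This also stands, and it is why the figures are an illustration. But 6.2 then plans a test on data that the study does not collect, and the contradiction remains.

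**The inputs are assumed.** The documents do not say that faculty score higher than trainees. At a faculty rate of 50%, the pooled test is positive less often (1.5%) than the trainee test (2.2%).

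**Faculty may be intended.** A reader might infer that faculty were put in by mistake. The documents do not show that; they show a conflict to be reconciled. Section 1.2 also counts trained faculty among the interview participants.

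**Conclusion.** The point holds in this form: as written, Ha1b is one test over trainees and their trainers, and a positive result need not mean that at least 50% of trainees met the criterion. The textual contradiction depends on no assumption.

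Its size does. With 13 faculty, 42 trainees, an exact one-sided 2.5% test and a true trainee rate of 50%, the chance of a positive test ranges from 1.5% to 32.2% as the faculty rate goes from 50% to 100%, against 2.2% in trainees alone. At the upper end, the trainee count needed falls from 28 to 23 of 42.

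This is a secondary, self-rated outcome, and the primary test is unaffected. The change is worth making because it is nearly free.

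**What to change.** - **6.2:** make the Ha1b test the proportion among residents and fellows. If faculty are surveyed, report their proportion separately with an exact confidence interval. State the level, the sidedness and the exact test for Ha1b.
- **6.3:** name residents and fellows as the population for the confidence test.
- **2, 3.3, 4.1 and 6.2:** reconcile who is in the confidence endpoint. If faculty are meant to be subjects, 4.1 and section 5 must say so and give their survey procedure.
- **3.3:** remove faculty from simulated-encounter performance unless a faculty procedure is added.
- **3.2:** resolve the same conflict in the primary endpoint, which lists faculty although 6.1 to 6.3 analyse trainees only.

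The cost is wording, plus a smaller n for this secondary proportion: 42 instead of 55 under the assumption above. The change does not make the criterion a measure of gain, because a post-intervention score of 4 or 5 still ignores baseline in trainees too.

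### Ha1b scores 'increased confidence' as a post-training rating of 4 or 5 and tests only that share, so it can miss a modest real rise and can declare an increase when none occurred

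*Combined protocol and SAP*

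**What the plan says.** Section 1.2 describes the instrument: "Using a 5 point Likert scale", participants "rate their confidence in various communication skills domains pre- and post-intervention via online survey". Three surveys are scheduled for trainees.

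- Three to four weeks before the elective, "they will be sent an email to complete an online confidence survey" (5.1).
- During the elective, after training: "participant sent electronic notification to take post intervention survey of confidence" (5.2).
- Later, "At four months, subjects will be asked electronically to complete their final confidence survey" (5.3).

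The hypothesis in section 2, Aim 1, is "Trainee and faculty confidence will increase after training for ≥50% of participants". Section 6.2 makes this operational by treating a post-intervention score of 4 or 5 as increased confidence. It will then "calculate proportion of subjects who have increased confidence and show 95% confidence intervals as well, then we will use a proportion test". Nothing else is planned for confidence. Section 6.2 does not say how the domains become one score, and it gives no alpha, sidedness, sample size or power for Ha1b.

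**The concern.** An increase is a comparison of after with before. The rule in 6.2 looks only at after, and only at which side of a cut the rating falls. Someone who moves from 1 to 3 counts as not increased. Someone who starts and stays at 4 counts as increased. The result therefore depends heavily on where trainees start, which the plan does not know and the test does not use.

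Confidence is a named secondary endpoint of Aim 1, and Ha1b is its only planned test. A trial report could say that confidence was not shown to rise when it did, or that it rose when it did not. The plan treats its other scored outcomes differently. Ha1c analyses full scores over repeated encounters with a linear mixed model, and the ERSQ total and emotional exhaustion scores are kept as continuous.

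**Working it through.** **Plan's own figure.** There is none for Ha1b. The 69.05% detectable proportion in 6.1 belongs to Ha1a; only its sample size, alpha and sidedness are borrowed here.

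**Inputs from the document.** n=42 trainees (6.1); null share 50% (section 2 and 6.2); 5-point scale (1.2); cut at 4 or 5 (6.2); one-sided 2.5% exact test, stated for Ha1a in 6.1 and assumed for Ha1b.

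**Inputs assumed.** One item. Pre and post ratings are correlated normal variables rounded and clipped to 1 to 5, with SD 0.9 and correlation 0.5 unless shown otherwise.

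**Step 1, rejection rule.** With X ~ Binomial(42, 0.5), P(X ≥ 27) = 4.42% and P(X ≥ 28) = 2.18%. At 2.5% the planned test rejects at 28 of 42 or more. A cut-off of 27 would raise every rejection rate below, false ones included.

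**Step 2, share at 4 or 5.** A rounded rating is 4 or more when the underlying value is at least 3.5, so share = Φ((mean − 3.5)/SD).

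- Mean 3.5, SD 0.9: Φ(0) = 50.0%
- Mean 3.8, SD 0.9: Φ(0.333) = 63.1%
- Mean 4.0, SD 0.9: Φ(0.556) = 71.1%
- Mean 4.0, SD 1.0: Φ(0.5) = 69.1%

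**Step 3, planned test.** P(X ≥ 28) at those shares is 2.2%, 37.8%, 79.1% and 70.2%. The pre-training mean does not enter, so these rates are the same whether or not anyone changed.

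**Step 4, paired alternatives.** These are simulated on the same model with thousands of replicates per row. McNemar on the same cut is included only to isolate the cost of the yes/no reduction; it is not in the plan.

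| Mean pre → post | Correlation | Share 4–5, pre → post | Planned test | Exact McNemar, same cut | Signed-rank, full scale |
|---|---|---|---|---|---|
| 3.0 → 3.5 | 0.3 | 29% → 50% | 2% | 51% | 78% |
| 3.0 → 3.5 | 0.5 | 29% → 50% | 2% | 56% | 89% |
| 3.0 → 3.5 | 0.7 | 29% → 50% | 2% | 66% | 97% |
| 3.2 → 3.6 | 0.5 | 37% → 54% | 7% | 40% | 71% |
| 3.0 → 4.0 | 0.5 | 29% → 71% | 79% | 99% | 100% |
| 3.8 → 3.8 | 0.5 | 63% → 63% | 38% | 1% | 2% |
| 4.0 → 4.0 (SD 1) | 0.5 | 69% → 69% | 70% | 1% | 3% |

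**Step 5, cost of the cut alone.** Signed-rank minus McNemar is 78 − 51 = 27, 89 − 56 = 33, 97 − 66 = 31 and 71 − 40 = 31 points for rises of 0.4 to 0.5. For a 1-point rise it is about 1 point.

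**Step 6, error rate of the alternative.** With no change, signed-rank rejects 2% to 3% of the time, so its advantage does not come from an inflated error rate.

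**The case against.** Four objections deserve an answer.

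- **The 2% is not low power.** At a post mean of 3.5 the true share is exactly 50%, so 2% is the planned test's size at its own null. This is correct. The test does what it was built to do; the fault is that its null is not 'confidence did not increase'.
- **A reader might infer that the plan gives up some 20 to 40 points of power and that a real rise is likely to be missed.** The documents do not support that. The figure compares a full-scale test with McNemar, which nobody plans. The rise, SD, correlation, starting level and number of items are all absent. A wider one-item grid at n=42 puts that gap anywhere from 1 to 67 points. A 1-point rise from 3.0 would be detected about 79% of the time as planned. With a high starting level the planned test can even reject more often than a paired test, but it also does so when nothing has changed.
- **The 50% benchmark is a deliberate share-of-learners question, parallel to Ha1a, and a mean change does not answer it.** This stands. A mean-change test can reject when fewer than half improve, so the benchmark should be kept beside the new test.
- **Redefining 'increased' as post above pre would be enough.** It would bring in the baseline, but ties and participants already at 5 would count as failures. Tested against 50%, it too rejects only about 2% of the time for a rise from 3.0 to 3.5.

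**Conclusion.** The concern holds in both directions. As written, Ha1b does not test whether confidence increased. Under the stated assumptions it would almost never report a half-point rise from 3.0 (2%, against 89% for signed-rank at correlation 0.5). It would report an increase 38% to 70% of the time in an unchanged group already averaging 3.8 to 4.0. The reduction to yes/no costs about 27 to 33 points for rises of 0.4 to 0.5 and close to nothing for a 1-point rise.

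These sizes are illustrations, because the plan supplies no planning values for confidence. That the test ignores the starting level needs no assumption: it follows from the definition in 6.2. The proportion and its interval will still be reported and remain informative about confidence after training. This is a secondary endpoint; the primary analysis is unaffected.

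**What to change.** In 6.2, for Ha1b:

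- Average the domain ratings to one score per participant at each survey.
- Test whether confidence increased with a paired full-scale analysis. Use either a signed-rank test of post minus pre, or the linear mixed model with random subject effect already specified for Ha1c, over the pre, post and four-month surveys. Choose one in advance and name the contrast that decides the hypothesis.
- Report the change with its 95% confidence interval.
- Keep the proportion rating 4 or 5, with its exact 95% interval against the 50% benchmark, as an accompanying result. Describe it as confident after training, not as increased.
- State alpha, sidedness and the number analysed, and whether faculty are included; the survey schedule in section 5 is written for trainees on the elective.

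The cost is SAP wording and one extra routine analysis of surveys already scheduled, with no added participants or burden. The mean change and the share benchmark answer different questions, so the report must keep the two apart.
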